Study Protocol Cover page

Title: Effectiveness, safety, and tolerability of different estradiol dosing regimens in transgender females.

NCT Number: NCT05010707

Date: May 26, 2022

Washington University in St. Louis

Version Date: May 26th, 2022

Principal Investigator: [name]

Study Title: Effectiveness, safety, and tolerability of different estradiol dosing regimens in transgender females.

Faculty Sponsor: [name]

- **Objectives**

The purpose of this open label, pilot, randomized clinical trial is to evaluate the effectiveness, safety and tolerability of estrogen use in transgender female and the degree of testosterone suppression achieved in this population when placed on sublingual 17-beta estradiol in comparison to transdermal 17-beta estradiol for gender affirming pharmacological therapy over the first two-years of treatment.

This study is important because, to our knowledge, this is the first randomized clinical trial evaluating the effectiveness, safety, and tolerability of estrogen in transgender female. There are no previous data comparing the different presentation of estrogen options in transgender women; therefore, this clinical trial will determine the best strategies and methods required to develop a larger randomized clinical trial. This study will also provide information useful to close the medical knowledge gap to provide safe and competent care to transgender female patients.

Aims

Aim 1. In this randomized clinical trial, we will evaluate the degree of testosterone suppression by measuring total testosterone level in transgender female patients undergoing hormonal affirming therapy randomized to sublingual 17 beta estradiol or transdermal 17 beta estradiol, in conjunction with spironolactone (antiandrogen), for a period of 2 years.

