Hypothesis 1a. Transgender females undergoing hormonal affirming therapy randomized to sublingual estradiol with multiple daily doses will have higher degree of testosterone suppression. This hypothesis is based on the rationale that higher peak levels obtained with sublingual estradiol will suppress the hypothalamic-pituitary axis to a greater degree than the more stable levels achieved with transdermal delivery. Multiple studies (15) (18) in cisgender women describe the daily biological rhythm of estradiol, and a diurnal cycle of estradiol exhibiting an early morning peak followed by two to four recurrent cycles. However, there is no information on transgender patients regarding best pharmacological intervention (continuous vs pulsatile) to suppress the hypothalamic-pituitary-gonadal axis.

Aim 2. In this randomized clinical trial, we will determine the impact on liver enzymes, metabolic profile, and thrombogenic factors in transgender female patients undergoing hormonal affirming therapy randomized to sublingual 17 beta estradiol or transdermal 17 beta estradiol, in conjunction with spironolactone (an antiandrogen), for a period of 2 years.

Hypothesis 2a. Transgender female patients on sublingual estradiol will have higher levels of estrone, which will lead to an increase on thrombogenic factors and changes in metabolic factors. It has been determined that higher estrone levels in cisgender females, has been linked with a high incidence of venous thromboembolism, breast cancer, and endothelial inflammation. An explanation for the higher thrombotic risk in postmenopausal women includes high production of thrombin due to high levels of estrone (12). Hypothesis 2b. Higher fat mass after FHT will have a negative impact on insulin sensitivity. Estradiol therapy in transgender women appears to be associated with an increase in fat mass and decrease in lean mass, although prospectively controlled data is limited (11). The increase in body fat associated with estrogen therapy raises questions about the effect on insulin sensitivity and cardiovascular risk.

Purpose, Background, and Rationale

- **Background and Significance**

Transgender individuals experience discordance between their self-identified gender and biological birth sex (1). Some transgender individuals experience gender dysphoria which the Diagnostic and Statistical Manual of Mental Disorders (DSM-5) defines as clinically significant distress or impairment in social, occupational, or

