The current approach to FHT is not uniform or FDA approved and depends on the health care system, cost considerations, and differences in the regional availability of estrogens and antiandrogens. A typical regimen includes estrogen to provide feminizing effects in conjunction with therapy to block testosterone (antiandrogens or gonadotropin-releasing hormone [GnRH] analogs). Estrogen also inhibits testosterone secretion (9)(13). Ethinyl estradiol was previously the mainstay of most estrogen-directed therapies; this is no longer the case due to its increased risk of cardiovascular death and increased incidence of deep venous thrombosis (7). 17-beta estradiol, which can be provided in tablet, patch, and injection, is currently the preferred formulation (8).

Androgen blockade is usually established in all transgender females undergoing feminizing therapy and is achieved by either using gonadotropin blockade or antiandrogens. The latter, defined as medications other than estradiol which are used to decrease the synthesis of or actions of androgens. In the United States, spironolactone is commonly prescribed. Cyproterone acetate (CPA) is not licensed for use in the United States; however, CPA appears to be favored in many European countries and forms standard care as part of the European Network for the Investigation of Gender Incongruence (ENIGI) treatment protocol (10).

- **Innovation**

Transgender female patients suffer from poor health outcomes compared with their cisgender peers, mostly because feminizing therapy with estrogen has been based on data from postmenopausal women and expert opinion. This represents a critical gap in knowledge that prevents the delivery of safe and appropriate care for the transgender population. This proposal is innovative because the project is aimed to study the tolerability, safety, and differences in testosterone suppression of the most common 17-beta estradiol presentation while using the same antiandrogen (spironolactone). Any differences detected between the groups will be attributed to the estrogen effect based on their route of administration. Moreover, this randomized clinical trial will allow the collection of valuable preliminary data to determine the best strategies and methods required to develop a larger randomized clinical trial. This knowledge will set the stage for future feasible and sustainable interventions for transgender youth to improve health related outcomes.

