- **Methods, Research Plan, and Design**

- **Study design**

This study will be a prospective 2-year randomized, open label, clinical trial, using daily dose sublingual versus twice daily dose sublingual versus transdermal 17-beta estradiol in transgender female patients. Primary outcome is degree of testosterone suppression. Secondary outcome to measure safety and tolerability will

include liver enzymes, thrombogenic, and metabolic factors. Patients will be evaluated every 6 months during the length of the study

b. Subjects

Inclusion criteria: Female transgender patients between the ages of 18 to 45 years of age who are seen at the Washington University Transgender Center. Patients must have met the eligibility and readiness criteria for gender-affirming hormone therapy.

Exclusion criteria: Use of GnRH agonist for the last 12 months, history of liver disease, dyslipidemia requiring treatment, drug use, alcohol use (>2drinks per day), cigarette smoking, history of blood clot (venous thromboembolism, pulmonary embolism), history of hyperkalemia, history of Addison's disease, concomitant use of eplerenone.

Patients who have been referred to the Washington University Transgender Center for feminizing hormonal therapy and meet the inclusion criteria, will undergo consent process before initial evaluation. Methods for recruitment includes phone calls, emails, letters, and EPIC slicer dicer. For consent, physical or electronic consent form will be provided.

If consent is obtained, patients will be assigned to either daily sublingual vs twice daily sublingual vs transdermal 17-beta estradiol. Assignment will be done through block randomization.. Using the inclusion criteria, our center provides care to 150-200 new transgender female patients in a year for initiation of female hormone therapy.

We aim to enroll a total of 70 patients. This is a pilot study, which results will guide the feasibility, design, and implementation of a larger clinical trial. To account for 15% of potential dropout, we have planned to enroll a total of 80 patients.

- Research Plan**

The proposed clinical trial involves 2 research aims to be conducted over two years (Table 1). Subjects will be recruited from the Washington University Transgender Center. The Center is projected to see more than 1,000 patients every year, of which 150-200 are new transgender female patients for initiation of FHT.

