Patients who agree to participate in the study and meet inclusion criteria will undergo the evaluation described in Table 2. Data of interest will be collected on all patients enrolled and will be saved on a database created in Research Electronic Data Capture (REDCap). Information to be collected will include:

1. Demographic and anthropometric variables: Parameters will be routinely collected through chart review.
2. Laboratory testing: During each visit, we will obtain hormone levels, coagulation factors, metabolic factors, electrolytes level. A hematologist will review the lab results and communicate any recommended interventions (including stopping medication) to the participant's treatment team.

Initial evaluation will include patient history, physical examination, and baseline labs. During the initial visit, patients will be started on spironolactone and 17-beta estradiol transdermal or or daily sublingual or twice daily sublingual based on their treatment group assignment. Our team will check hormonal levels every 4 weeks (+/- 2 weeks) until estradiol level is within goal (see dosing guidelines) as established by standard of care. Once patients are started on estradiol, they will be asked to attend 6 more visits for the 2 years duration of the study as described in table 2.

Dosing guidelines:

Per the current standard of treatment, all study medications are initiated at the lowest available clinical dose and titrated to effectiveness at the study clinician's discretion by 6 months of study participation, using plasma total testosterone level in the cisgender female range (<50ng/dL) with serum estradiol level that should not excess the peak physiologic range 100-200 pg/mL. In some cases, medication doses will be titrated at monthly study follow up visits to optimize treatment response.

Spironolactone:

Starting dose will be 50 mg daily

Plan to increase 50 mg monthly to standard dose of 200 mg daily

For patients randomized to transdermal (patch) estradiol:

Starting dose will be 100 mcg/24hrs

Plan to increase by 100 mcg/24hrs every month

Max dose 400 mcg/24hrs

Goal is to achieve a serum estradiol level between 100-200 pg/mL and to suppress testosterone to cisgender female levels

Estradiol levels will be measured in the morning (fasting sample)

For patients randomized to daily sublingual estradiol:

Starting dose will be 2 mg daily

Plan to increase every month by 2 mg daily

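### The protocol credits any group difference to route of administration, but the design supports only a comparison of titrated regimens

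*Combined protocol and SAP*

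**What the plan says.** The interpretive statement is in the Innovation section: "Any differences detected between the groups will be attributed to the estrogen effect based on their route of administration". The sentence before it notes that all groups receive the same antiandrogen, spironolactone.

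The Study design section describes an open-label trial "using daily dose sublingual versus twice daily dose sublingual versus transdermal 17-beta estradiol in transgender female patients" and adds: "Primary outcome is degree of testosterone suppression".

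Under Dosing guidelines, "all study medications are initiated at the lowest available clinical dose and titrated to effectiveness at the study" clinician's discretion over the first 6 months. The guide is a "testosterone level in the cisgender female range (<50ng/dL) with serum estradiol level that should not excess the peak physiologic range" of 100-200 pg/mL. The sublingual arms both start at 2 mg a day in total (2 mg once, or 1 mg twice) and rise by 2 mg a day each month. The patch starts at 100 mcg/24 h and rises monthly by the same amount to a maximum of 400. No maximum appears for the sublingual arms. Spironolactone has one written schedule for everyone, 50 mg rising monthly to 200 mg. Estradiol is read from a fasting morning sample, with no stated time since the last dose.

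Elsewhere the protocol treats frequency as a question in its own right. The title is "Effectiveness, safety, and tolerability of different estradiol dosing regimens in transgender females". Hypothesis 1a expects that "sublingual estradiol with multiple daily doses will have higher degree of testosterone suppression", and it notes the lack of information on the "best pharmacological intervention (continuous vs pulsatile) to suppress the hypothalamic-pituitary-gonadal axis".

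**The concern.** Read literally, the sentence assigns every difference to one cause, while the arms differ in more than one respect. A difference between the two sublingual arms would be labelled a route effect although the route is the same. A difference between a sublingual arm and the patch, or the lack of one, would be credited to route alone although it also reflects how often the drug was taken and what dose the clinician settled on.

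This matters because the pilot is meant to guide the design of a larger trial. If a sublingual versus transdermal result is passed on as a pure route effect, the planners may carry forward a route when what was tested was a route at a particular frequency and titrated dose.

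**Working it through.** No figure in the plan bears on this point, so the main check sets the sections side by side. A short calculation on sample timing follows, as an illustration only.

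**Step 1: what differs in each contrast.** Three arms give 3 pairwise contrasts (Study design, Dosing guidelines).

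| Contrast | Route differs | Frequency or pattern differs | Dose reached can differ |
|---|---|---|---|
| Once-daily vs twice-daily sublingual | No | Yes | Yes |
| Once-daily sublingual vs patch | Yes | Yes | Yes |
| Twice-daily sublingual vs patch | Yes | Yes | Yes |

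One contrast of three has no route difference, and none differs in route alone.

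**Step 2: how dose enters.** The outcome is testosterone suppression. The same variable, with estradiol, tells an unblinded clinician when to raise the dose. Testosterone at follow-up is therefore a result of the assigned form and frequency together with the dose to which they led. Spironolactone has a common schedule but falls under the same discretion, so the same drug does not guarantee the same dose.

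**Step 3: whether later text corrects the sentence.** The Statistical methods section names an independent t-test between treatment groups, with a rank-sum test as fallback. It names no primary contrast, does not say whether the sublingual arms are pooled, and does not say how a difference will be interpreted.

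**Step 4: sample timing in the sublingual arms (separate, illustrative).** The assumptions, none from the documents, are one compartment, immediate absorption, steady state, linearity in dose, equal total daily dose, and a half-life h of 3 to 18 hours. Let x = 2^(-12/h).

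- Twice-daily reading divided by once-daily reading, both just before a dose: 0.5(1 + x)/x.
- The same ratio, both drawn at the same interval (up to 12 h) after a dose: 0.5(1 + x).
- Within the once-daily arm, a draw at 12 h divided by a draw at 24 h: 1/x.

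| h (hours) | x | Pre-dose ratio | Same-interval ratio | 12 h / 24 h, once daily |
|---|---|---|---|---|
| 3 | 0.0625 | 8.5 | 0.53 | 16 |
| 6 | 0.25 | 2.5 | 0.63 | 4 |
| 12 | 0.50 | 1.5 | 0.75 | 2 |
| 18 | 0.63 | 1.3 | 0.81 | 1.6 |

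The two ratios lie on opposite sides of 1 throughout. The estradiol goal of 100-200 pg/mL spans a factor of only 2.

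To see the effect on dose, take h = 6 and the written steps: start at 2 mg and add 2 mg at months 1 to 5 while the reading is below 100 pg/mL. Assume that estradiol alone ends titration and that the twice-daily reading is 20, 30 or 40 pg/mL per mg.

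- Twice daily: stops at 6, 4 or 4 mg (readings 120, 120, 160).
- Once daily, pre-dose draws: divide by 2.5 to get 8, 12 or 16 per mg. The arm reaches 12 mg (still 96), 10 mg (120) or 8 mg (128).
- Once daily, same-interval draws: divide by 0.625 to get 32, 48 or 64 per mg. The arm stops at 4 mg (128), 4 mg (192) or 2 mg (128).

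Draw time alone can thus decide which sublingual arm ends on the higher dose. These figures concern estradiol readings and doses in the two sublingual arms. They say nothing about the patch and are not testosterone effects.

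**The case against.** There is a fair case for the protocol. The sentence follows the remark that the antiandrogen is common to all groups, so it may only mean that differences come from the estrogen side of the regimen. The single spironolactone schedule partly supports that. The sentence is also narrative, not an analysis rule, and the title and Hypothesis 1a show that the investigators know frequency is under study. Finally, tablets in mg and patches in mcg/24 h share no dose scale in these documents, so titrating to a common target is a sensible way to compare them, and the dose reached is part of the regimen.

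Most of this stands. Titration to target is legitimate, and randomisation protects the comparison of titrated regimens. But the sentence goes on to name route, it covers any difference, and it is the only statement in the documents of how differences will be read.

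Two stronger inferences should be resisted. A reader might infer that the daily versus twice-daily result could push planners towards the wrong route. It could not by itself, since both sides have the same route; frequency affects a choice of route only through comparisons with the patch, or through pooling, on which the documents are silent. A reader might also infer that titrating on the outcome must shrink a testosterone difference by some calculable amount. The documents fix neither direction nor size: depending on which reading drives the dose, a difference could narrow, widen or reverse.

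**Conclusion.** The attribution to route goes further than the design allows and should be changed. What is certain from the text is that one of three contrasts has the same route on both sides and that the other two also carry frequency and titrated dose. This part rests on no assumption. The trial can still answer which titrated regimen lowers testosterone more.

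The size of any misattribution in the sublingual versus transdermal contrasts is unknown. The unstated dose-to-draw interval is a separate operational gap: closing it would not rescue the attribution, and rewording the sentence would not close it. A reader might take the timing ratios as a measure of bias in the primary outcome; they are not, since they come from an assumed model and half-life and compare only the two sublingual arms.

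**What to change.** 1. Reword the Innovation sentence, for example: Differences between groups will be interpreted as differences between the titrated regimens (estradiol form and frequency, with spironolactone as given). Daily versus twice-daily sublingual estradiol is a contrast of dosing frequency.
2. Record the current estradiol and spironolactone dose as a study data field at each visit, and report both by arm beside testosterone at 6, 12, 18 and 24 months. The Research Plan's list of data names demographic and anthropometric variables (from chart review) and laboratory tests; dose is not on it, so it should not be left to chart review.
3. Separately, replace the untimed morning sample in each sublingual arm with one fixed dose-to-draw interval, chosen by the investigators, and record the time of the last estradiol dose at every draw. This makes readings consistent within an arm. It does not equalise exposure between arms, so the interval should be reported with the level.

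Arms, targets, sample size and test stay as they are. The cost is one sentence, a few data fields, one descriptive table, some coordination of draw times and a less strongly stated conclusion.

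### Eligibility bars recent GnRH agonist use but not prior estrogen, antiandrogens or gonadectomy, so a trial meant for new starters can admit patients whose testosterone is already low

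*Combined protocol and SAP*

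**What the plan says.** The study design section states: "Primary outcome is degree of testosterone suppression". The Objectives place the comparison "over the first two-years of treatment".

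The Subjects section has two inclusion statements: "Female transgender patients between the ages of 18 to 45 years of age who are seen at the Washington University Transgender Center" and "Patients must have met the eligibility and readiness criteria for gender-affirming hormone therapy". Its exclusions open with "Exclusion criteria: Use of GnRH agonist for the last 12 months". They continue through liver disease, treated dyslipidemia, drug, alcohol and tobacco use, and blood clots, and end with "history of hyperkalemia, history of Addison's disease, concomitant use of eplerenone".

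Background and Significance describes usual care: "A typical regimen includes estrogen to provide feminizing effects in conjunction with therapy to block testosterone", the blocking therapy being antiandrogens or GnRH analogs. It adds: "Estrogen also inhibits testosterone secretion". It also notes that spironolactone is in common use in the United States.

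The Statistical methods section names an independent t-test, or a Wilcoxon rank sum test if the data are non-normal. It names no covariate. Assignment is by block randomization, with no stratification factor given.

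**The concern.** The question is about starting treatment, so the natural population is people whose testosterone has not yet been lowered. The criteria remove one class of testosterone-lowering therapy and are silent on the others that the Background itself describes, two of which (estradiol and spironolactone) are the study drugs. A patient who is new to this Center may have been treated elsewhere.

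Three things are at stake:

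- **The primary contrast.** A patient who enters with little testosterone left to suppress contributes little or nothing to a difference in degree of suppression.
- **Balance.** With small arms and no adjustment or stratification, a few more such patients in one arm can move that arm's mean. The Innovation section would attribute any group difference to the route of estrogen.
- **Safety baselines.** Liver, metabolic and thrombogenic measures taken at entry would not be pre-treatment values in patients already on estrogen.

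**Working it through.** **Step 1. What the criteria cover.** This comes from reading the whole eligibility text in Subjects.

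| Prior state | Addressed by a criterion? |
|---|---|
| GnRH agonist, last 12 months | Yes, excluded |
| Estrogen, current or recent | No |
| Spironolactone or another antiandrogen, current or recent | No |
| Gonadectomy | No; not mentioned anywhere in the document |
| Low testosterone at entry | No; no minimum is set |

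**Step 2. What points to new starters.** The Objectives refer to the first two years. Subjects speaks of referral for feminizing therapy and of 150-200 new patients a year beginning it. The Research Plan has both drugs started at the initial visit. These are objective, feasibility and procedure statements. The inclusion criterion itself reaches anyone seen at the Center, and the contingency plan under Limitations would add patients from a second clinic without restating that they must be starting therapy.

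**Step 3. The plan's own figures.** The only sample-size figures are 70 patients, 15% dropout and 80 enrolled. 70 × 1.15 = 80.5, which agrees with 80 to rounding. The 70 cannot be re-derived, because no alpha, power, SD or target difference is given. The share of pre-treated patients is not given either. What follows is therefore illustration, with an assumed share p of 5%, 10% or 20%, three equal arms (n = 80/3 = 26.7), and a pairwise two-sided 5% test under a normal approximation.

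**Step 4. Upper bound on dilution.** Let δ be the arm difference in new starters, and let a share p have no possible arm difference. The expected difference is (1 − p)δ + p × 0 = (1 − p)δ.

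If the SD is also unchanged, the sample needed for the same power is multiplied by 1/(1 − p)². For a δ that would have had 80% power (2.802 × √(2/26.7) = 0.77 SD), power becomes Φ[(1.960 + 0.842)(1 − p) − 1.960].

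| p | Expected difference | Sample multiplier | Power |
|---|---|---|---|
| 5% | 0.95δ | 1.11 | Φ(0.702) = 76% |
| 10% | 0.90δ | 1.23 | Φ(0.562) = 71% |
| 20% | 0.80δ | 1.56 | Φ(0.282) = 61% |

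**Step 5. Why the dilution is an upper bound.** If pre-treated patients keep a fraction k of the route effect, the expected difference is [1 − p(1 − k)]δ. With p = 20% and an assumed k = 0.5, that is 0.90δ, not 0.80δ. Using change from baseline does not alter this, because randomization makes baseline equal in expectation. The SD is a separate matter and could move either way. Patients at the floor narrow the spread of attained levels, while mixing treated and untreated patients widens the spread of change from baseline.

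**Step 6. Chance imbalance.** The SD of the difference between two arms in the share of such patients is √(2p(1 − p)/n).

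- p = 5%: √(0.095/26.7) = 6.0 percentage points, or 1.6 patients per arm.
- p = 10%: √(0.18/26.7) = 8.2 points, or 2.2 patients.
- p = 20%: √(0.32/26.7) = 11.0 points, or 2.9 patients.

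**The case against.** The strongest reply is intent. The statements in step 2 describe an initiation trial, and Subjects ties its estimate of 150-200 initiators to the inclusion criteria. On that reading, pre-treated patients would rarely enter and the gap is one of wording. This stands to the extent that it makes such entry less likely. It does not bar it, because none of those statements is a criterion.

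A second reply also has force. A reader might infer that any previously treated patient cannot show suppression in any arm. The documents do not support that. Aim 1 measures total testosterone on the assigned regimen, so a patient with intact gonads who used hormones before can still reach a different level by route. Someone who stopped earlier may not be suppressed at all. The Background says that estrogen inhibits testosterone secretion, but it defines antiandrogens as reducing either the synthesis or the actions of androgens, so prior antiandrogen use need not mean a low level. The zero-difference case fits only patients after gonadectomy or those already fully suppressed.

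A third reply is that randomization protects the comparison. It does protect against systematic bias, and only chance imbalance remains.

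Finally, this is a pilot with no power calculation, so the power figures have no reference point in the plan. That is correct, and they are offered only for scale.

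**Conclusion.** The point holds as a gap between the intended population and the written one. Among prior testosterone-lowering treatments only recent GnRH agonist use is excluded, and nothing in the stated randomization or analysis compensates. It is worth correcting but is not a fatal flaw.

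Its size is unknown. The shrinkage to 95% to 80% rests on an assumed 5-20% share and on no arm difference in any of those patients. The multipliers and power figures also need an unchanged SD. The documents support none of these values.

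Three stronger readings should be resisted:

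- GnRH agonist use is not the only exclusion in the protocol; it is the only one concerning prior testosterone-lowering treatment.
- The GnRH line might suggest that the sponsor recognised prior suppression as a problem and overlooked the rest, but no reason for that line is given.
- The figure of more than 1,000 patients a year against 150-200 initiators does not give a pre-treated share, because the larger number is not limited to transgender women.

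**What to change.** Extend the existing exclusion line to current or recent estrogen use, current or recent antiandrogen use, and prior gonadectomy. The sponsor should set and justify the look-back window for estrogen and antiandrogens. Nothing in the documents shows that the 12 months used for GnRH agonists carries over. Confirm eligibility from the history taken at the initial evaluation and the baseline hormone levels in Table 2.

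Recording prior therapy and adjusting for baseline testosterone would be a useful addition. It deals with chance imbalance, but it does not restore the contrast lost in patients with nothing left to suppress, nor a clean pre-treatment baseline for safety. It is therefore weaker as a substitute.

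The cost is one line of text and no new measurements. The downside is a somewhat smaller pool in a trial that already lists recruitment as a limitation. Against that, 80 places are to be filled from 150-200 patients a year said to be starting therapy.

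### If 70 is the intended number of completers, enrolling 80 at the stated 15% dropout leaves an expected 68; 80 covers only 12.5% dropout

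*Combined protocol and SAP*

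**What the plan says.** The sample size appears in one place, section b (Subjects) of the combined protocol and SAP, under Methods, Research Plan, and Design. Three consecutive sentences deal with it:

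- The first figure: "We aim to enroll a total of 70 patients".
- The justification: "This is a pilot study, which results will guide the feasibility, design, and implementation of a larger clinical trial".
- The second figure: "To account for 15% of potential dropout, we have planned to enroll a total of 80 patients".

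Both 70 and 80 are described as enrolment. Neither is called completers, evaluable patients or a required minimum. The same section sets out three arms: "patients will be assigned to either daily sublingual vs twice daily sublingual vs transdermal 17-beta estradiol". It specifies block randomization but gives no allocation ratio. The section on statistical methods and data analysis gives no basis for the sample size, and nothing elsewhere restates or corrects either figure.

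**The concern.** A trial cannot have two planned enrolment totals, so the text needs clarifying before any arithmetic is done. The dropout sentence suggests the intended meaning: 80 is enrolled so that 70 remain. If so, the three numbers (70, 15% and 80) should satisfy one simple relation, and they do not.

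Little is at stake for inference. The plan states no power, effect size, standard deviation, precision target or minimum evaluable number, so no stated operating characteristic changes if 68 patients finish instead of 70. What is affected is the pilot's own purpose. Its results are meant to inform the feasibility and design of a larger trial, and retention is a natural feasibility measure. A plan that states 15% while its numbers imply 12.5% leaves unclear how many patients were expected to finish. The same inflation method, carried into the larger trial, would fall short there too.

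**Working it through.** **Inputs**, all from section b (Subjects):

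- N₀ = 70, read here as the number intended to complete. This label is inferred; the text does not state it.
- d = 15% dropout, read in the usual way as a fraction of those enrolled.
- N = 80, planned enrolment.

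**Step 1. Reproduce the plan's 80.** Adding 15% to the base gives N₀ × (1 + d) = 70 × 1.15 = 80.5. This is within one patient of 80 and is the likely origin of the figure. It applies the 15% to the 70 instead of to the patients enrolled.

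**Step 2. Expected completers from 80.** Dropouts: 80 × 0.15 = 12. Completers: 80 − 12 = 68. Shortfall: 70 − 68 = 2, and 2/70 = 2.9%.

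**Step 3. Dropout that 80 covers.** Losses allowed: 80 − 70 = 10. Rate: 10/80 = 12.5%.

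**Step 4. Enrolment needed for an expected 70 at 15%.** N₀/(1 − d) = 70/0.85 = 82.35, rounded up to 83. Check: 82 × 0.85 = 69.7, just below 70; 83 × 0.85 = 70.55.

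| Enrolled | Dropout | Expected completers |
|---|---|---|
| 80 | 15% | 68 |
| 80 | 12.5% | 70 |
| 83 | 15% | 70.55 |

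**Step 5. Scale of the gap.** Assume that patients drop out independently with probability 0.15. The binomial probability of at least 70 completers is then about 0.33 with 80 enrolled and about 0.64 with 83. The standard deviation of the number completing from 80 is √(80 × 0.85 × 0.15) = √10.2 ≈ 3.2, so the gap of 2 is about 0.6 of a standard deviation. With equal allocation to the three arms (also an assumption), the gap is 2/3, or about 0.7 of a patient per arm.

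**The case against.** The strongest case against has three parts.

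**The label is inferred.** The text says enrolment for both figures and never calls 70 completers. That is true, and the finding is conditional for this reason. However, no better reading of the 70 is available: if it is not the number left after dropout, the plan simply has two conflicting enrolment totals, which also needs correcting.

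**The denominator of the 15% is not defined.** Read as padding of about 15% on top of 70, the plan gives 80.5, and 80 is then consistent apart from rounding down. This explains where the 80 came from. It does not make the statement right, because a dropout rate ordinarily refers to those who entered, and at that rate 80 does not leave 70. Rounding does not rescue it either: 82.35 goes to 82 or 83, never to 80.

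**Nothing depends on two patients.** This stands in full. The 70 has no stated derivation, the 15% is given without a source, and the gap is well within chance variation. The plan also sets no retention criterion, and observed retention could be compared with the stated 15% directly. That limits the point to internal consistency and keeps it at the lowest severity.

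**Conclusion.** The concern holds, as a minor arithmetic inconsistency. Reading 70 as intended completers and 15% as a fraction of those enrolled, the plan's own numbers deliver an expected 68, or they support 12.5% dropout where 15% is stated. The arithmetic is exact; the only judgement is the meaning of the unlabelled 70, and the dropout sentence points clearly to completers. The trial's validity and its ability to address its aims are not affected.

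**What to change.** Replace the two sentences that carry 70 and 80 with one that keeps the sponsor's enrolment and dropout rate, for example: *Planned enrolment is 80 patients; at 15% dropout, about 68 are expected to complete.*

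If the sponsor prefers to keep 70, it should label that figure as the number expected to complete and state the 12.5% dropout that 80 supports, provided it can justify that rate. The rate should not be changed merely to make the sum work.

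Either version is an edit to two sentences, with no added patients and no change to procedures. Enrolling 83 would keep both the 70 and the 15%, but it enlarges the trial to protect a figure for which the plan gives no derivation, so it is not needed to correct the text.
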